4.9.1.4 Multiple Comparisons/Multiplicity

The overall type I family-wise error rate will be preserved at the one-tailed 0.025 nominal level (i.e. $\alpha = 0.025$) by controlling multiplicity over the two co-primary endpoints and over the two study targets (superiority and non-inferiority) using a multiple-sequence gatekeeping procedure (Keays et al., 1991). To achieve this, the analyses on primary endpoints will be grouped into two family of comparisons (gatekeepers) and processed as follows:

1. The first gatekeeper includes the superiority contrasts “NAC vs placebo” with the adjustment for multiple comparisons across the two co-primary endpoints performed according to Bonferroni. This implies that a difference will be considered statistically significant for a one-tailed p-value ≤ 0.0125 (i.e. $\alpha/2 = 0.0125$).
The transition to the second gatekeeper requires that at least one of the two co-primary endpoints is statistically significant in the mITT population.
2. The second gatekeeper includes the family of non-inferiority contrasts “NAC vs ambroxol” conducted for both the mITT population and PP population.
The analyses in the second gatekeeper will be performed depending upon the results obtained in the first gatekeeper as shown below:
 - a. If both superiority contrasts are found statistically significant in the mITT population, non-inferiority will be tested on both co-primary endpoints for both the mITT and PP populations with an overall probability α set to 0.025 (one-tailed) and with the adjustment for multiple comparisons across the two co-primary endpoints performed according to Hochberg. Details of the Hochberg procedure can be found in Appendix (Section 4.14.1).
 - b. If only one of the two superiority contrasts are found statistically significant in the mITT population, non-inferiority will be tested for that co-primary endpoint only for both the mITT and PP populations and will be considered achieved if the associated one-tailed p-values are ≤ 0.0125 .

Statistically significant results will be needed in both the mITT and PP populations to accept the hypothesis of non-inferiority of NAC versus ambroxol.

Consistent with the hypothesis testing process performed on the co-primary endpoints, the strategy described above will also be applied to control the coverage of confidence intervals at the two-tailed 95% nominal level (i.e. $1 - 2\alpha = 0.95$).

The analyses on secondary efficacy endpoints (not key) will be performed only to support primary endpoints findings and/or for explorative reasons, therefore no adjustment of significance level will be made to account for multiple comparisons.

4.9.1.5 Interim Analyses

No interim analysis will be performed.

4.9.1.6 Examination of Subgroups

Upon completion of the study, the study statistician in consultation with Zambon's Clinical Team will determine the proportion of concomitant medications between the treatment groups and will decide whether to perform subgroup efficacy analyses if deemed appropriate. The analyses described for the primary and secondary efficacy endpoints will be performed separately for each of the identified strata.

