12. PRIOR AND CONCOMITANT TREATMENTS

At Visit 1 (Screening), all prior and concomitant medications, including antibiotics, and over-the-counter products used by an individual subject within 1 month prior to Screening Visit (Visit 1) will be documented in the eCRF.

During all subsequent clinical visits, the Investigator will document any changes in concomitant medications.

The following concomitant treatments are permitted from Visit 1 to Visit 4 (end of IMP treatment) or unscheduled Deterioration Visit:

- Appropriate treatment(s) for any respiratory tract disease, that in the investigator's opinion will not interfere with the measurements contributing to the efficacy outcomes, such as: corticosteroids (inhaled or systemic), bronchodilators, antibiotics (in case of co-administration, the i.v. antibiotic should be administered separately).
- Appropriate treatment(s) for any other underlying disease, that in the investigator's opinion will not interfere with the measurements contributing to the efficacy outcomes
- If co-treatment with parenteral nitroglycerin is needed the patients should be monitored for potential hypotension, which may be severe and may be indicated by the presence of headache
- If one or more treatments interfering with the measurements contributing to the primary efficacy outcomes are deemed necessary, the patient should not be randomized or should be discontinued from the study

The following concomitant treatments are not permitted from Visit 1 to Visit 4 (end of IMP treatment) or unscheduled Deterioration Visit:

- Expectorants
- Antitussive agents
- Sedatives
- Traditional Chinese Medicine (TCM) treatments.

All concomitant medications will be recorded and analysed as described in [Section 20.4.3.3](#).

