4.7 Prior and Concomitant Medication

Medication start and stop dates will be compared to the date of first dose of study medication to allow medications to be classified as either Prior, or Concomitant.

Medications that start and stop prior to the date of first dose of study medication will be classified as Prior medication. If a medication stops on or after the date of first dose of study medication up to the last dose of study medication, then the medication will be classified as a Concomitant medication.

If medication start and/or stop dates are missing or partial, the dates will be compared as far as possible with the date of first dose of study medication. Medications will be assumed to be Concomitant, unless there is clear evidence (through comparison of partial dates) to suggest that the medication stopped prior to the first dose of study medication. If there is clear evidence to suggest that the medication stopped prior to the first dose of study medication, the medication will be assumed to be Prior.

Imputation of partial dates of prior and concomitant medications is described in Appendix 4.14 (section 4.14.7).

Prior and concomitant medication will be summarized using the ITT population (Section 4.4.2) separately. Frequency table will be provided by treatment group, anatomical therapeutic chemical (ATC) drug class and preferred term (PT), where ATC and PT will be coded using the World Health Organization-Drug Dictionary Enhanced (WHO-DDE) September 2020 B3.

A by-subject listing of prior and concomitant medications will be provided using the ITT population.

In addition, the following treatments are not permitted from Visit 1 to Visit 4 (end of IMP treatment) or unscheduled Deterioration Visit:

- Expectorants
- Antitussive agents
- Sedatives
- Traditional Chinese Medicine (TCM) treatments.

Prior prohibited medications are defined as those prohibited medications with a stop date on or after the Visit 1 date, and prior to the first dose of study medication date. Prohibited concomitant medications are defined above as for concomitant medications for those treatments not permitted.

Prior prohibited medications and prohibited concomitant medications will be summarized for the ITT population. Frequency tables will be provided following the same structure as for prior and concomitant medications.

A by-subject listing of prohibited medications will be provided using the ITT population.

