	Missing	
The same imputation rule of partial start date when start date is partial, stop date is known will be applied;
 
The stop date will not be imputed.
 
Considered as concomitant.

Start Date	Stop Date	Action
Missing	Known	
The date of first dose will be used if stop date is not prior to the date of first dose of study medication.
 
Start date will not be imputed if stop date is prior to the date of first dose of study medication.
 
If stop date is prior to the date of first dose of study medication, considered as prior;
 
if stop date is on or after the date of first dose of study medication, considered as concomitant.

	Partial	
Start date will not be imputed;
 
the same imputation rule of partial stop date when start date is known, stop date is partial will be applied.
 
If the imputed stop date is prior to the date of first dose of study medication, considered as prior;
 
if the imputed stop date is on or after the date of first dose of study medication, considered as concomitant.

	Missing	
The date of first dose will be used to impute start date;
 
the stop date will not be imputed.
 
Considered as concomitant.

Note: If the recorded start date or imputed start date of the medication is after the date of last dose of study drug, it will not be classified to prior or concomitant medications, just set the category to missing.

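### Concomitant-medication subgroups are chosen after the study ends and can rest on medication started during treatment, so trigger and strata may themselves be affected by treatment

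*SAP*

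**What the plan says.** SAP 4.9.1.6 sets the time and the deciders: "Upon completion of the study, the study statistician in consultation with" the sponsor's clinical team. Together they "will determine the proportion of concomitant medications between the treatment groups and will decide whether to perform subgroup efficacy analyses if deemed appropriate". If they go ahead, "The analyses described for the primary and secondary efficacy endpoints will be performed separately for each of the identified strata". Protocol 20.4.3.3 (version 2.0) carries the same rule, and Protocol 12 refers the analysis of all concomitant medication to it.

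SAP 4.7 classes a medicine as concomitant by its stop date: it qualifies if it "stops on or after the date of first dose of study medication up to the last dose of study medication". The only limit on start date is the note under the table in SAP 4.14.7.1, which leaves a medicine unclassified "If the recorded start date or imputed start date of the medication is after the date of last dose of study drug".

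Protocol 12 permits respiratory treatments such as "corticosteroids (inhaled or systemic), bronchodilators, antibiotics" during the treatment week and has changes recorded at each later visit.

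By contrast, Protocol 20.4.6 requires the pooling of sites to be settled after the study is complete but before unblinding. The subgroup rule has no such condition.

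**The concern.** A subgroup comparison keeps the protection of randomisation only if subgroup membership could not have been affected by the assigned treatment. Medication ongoing at the first dose meets that condition; medication added on Day 4 may not. If patients whose sputum is not improving are more likely to get an added antibiotic, steroid or bronchodilator, and NAC changes who improves, then use differs between arms because of the drug. That difference is what prompts the subgroup analysis, and each stratum then compares arms selected on early response.

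A second route does not need a drug effect. Protocol 10.2 describes the staff who give study drug as unblinded and also responsible for patient care, while Protocol 13.2 says the administering staff are not involved in care. These passages must be reconciled. Until they are, prescribing that depends on known allocation cannot be excluded.

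The amendment log records that the analysis was added at the regulator's suggestion, so its results are likely to be read closely. A distorted stratum result could make a real effect look explained by co-medication, or produce a subgroup finding that is not there.

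**Working it through.** **1. Do on-treatment starts count?** Take an antibiotic started on Day 4 and stopped on Day 7. Its stop date is after the first dose and not after the last, so SAP 4.7 makes it concomitant. Its start is not after the last dose, so the note in 4.14.7.1 does not remove it. It counts, as does a medicine ongoing since before randomisation. The strata are therefore a mixture of baseline and on-treatment use.

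**2. Design figures.** SAP 4.9.1.6 states no number. The inputs below come from SAP 4.11: effect 0.35, SDs 0.79 and 0.77, correlation 0.31, margin 0.30, 100 evaluable per arm. A 4,000-run simulation with these gives 93.2% disjunctive superiority power (stated: close to 93%) and 81.0% gated non-inferiority power (stated: 82%, taking a true difference of 0). 300/0.9 = 333.3 (stated: 333). The inputs are thus used as the plan uses them.

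**3. Effect by stratum when medication follows response.** Assumptions, none given in the documents: Day-3 and Day-7 changes are bivariate normal with SD s = 0.78 and correlation ρ = 0.5–0.7; the NAC effect is 0.2–0.3 at Day 3 and 0.35 at Day 7 in everyone; new medication goes to the 30% with the poorest Day-3 change. Let z be the standardised cut-off in an arm (N = NAC, P = placebo), p the share above it and φ the normal density:

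- Users: 0.35 − ρs[φ(zN)/pN − φ(zP)/pP]
- Non-users: 0.35 − ρs[φ(zP)/(1−pP) − φ(zN)/(1−pN)]

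For a Day-3 effect of 0.3 and ρ = 0.7: ρs = 0.546, pN = 0.234, pP = 0.366, φ(zN) = 0.3066, φ(zP) = 0.3762.

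- Users: 0.35 − 0.546 × (1.310 − 1.028) = 0.20
- Non-users: 0.35 − 0.546 × (0.593 − 0.400) = 0.24

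Now add the baseline users whom SAP 4.7 also counts: a share b, equal in both arms and unrelated to response. Non-users are unchanged. Users become 0.35 − ρs(1−b)[φ(zN)/(b+(1−b)pN) − φ(zP)/(b+(1−b)pP)]. With b = 0.4:

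- Users: 0.35 − 0.3276 × (0.3066/0.5404 − 0.3762/0.6196) = 0.35 + 0.013 = 0.36

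A uniform effect of 0.35 now reads as 0.36 in users and 0.24 in non-users.

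| Scenario (true effect 0.35 throughout) | Users | Non-users |
|---|---|---|
| Only new medication, Day-3 cut-off | 0.20–0.28 | 0.24–0.30 |
| Same, plus 40–70% baseline use | 0.35–0.36 | 0.24–0.30 |
| Only new medication, logistic prescribing (odds ratio 1.6–2.7 per SD of Day-3 response) | 0.31–0.35 | 0.31–0.35 |
| Strata by baseline use only | 0.35 | 0.35 |

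**4. Error rate when use differs for another reason.** The true effect is 0, with 111 per arm and nominal one-sided 0.025. Medication goes to the patients with the worst latent prognosis (correlation 0.3–0.5 with the Day-7 change), and the share treated is set separately in each arm:

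| Use, placebo vs NAC | Rejection rate per stratum | Bias (points) |
|---|---|---|
| 40% vs 40% | 0.019–0.031 | about 0 |
| 30% vs 40% | 0.04–0.07 | 0.03–0.08 in favour of NAC |
| 30% vs 50% | 0.07–0.14 | 0.07–0.14 in favour of NAC |
| 50% vs 30% | 0.002–0.009 | 0.07–0.14 against NAC |

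In the last case a true effect of 0.35 appears as 0.21–0.28. The sign of the bias follows the direction of the difference in use.

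**The case against.** The strongest reply has four parts.

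- **Size.** The large shortfalls need a hard cut-off and no baseline users. With baseline use equal in both arms, the user stratum sits at or slightly above the truth, and the between-arm gap in use, which is the trigger, shrinks from 9–13 points to 5–8 at 40% baseline use and 1–4 at 70–85%. With logistic prescribing the bias is only 1–11%. This stands. A reader might infer that the rule understates the NAC effect in every stratum; the plan's definition of concomitant medication does not support that.
- **Pathway.** Protocol 12 permits only treatments that the investigator judges not to interfere with the efficacy measurements, and otherwise calls for discontinuation. Patients given rescue mucolytic are also withdrawn, and missing scores are then imputed by the worst observation. This narrows the route, and the calculations above ignore it. It does not close it: the named respiratory classes stay permitted, and the judgement is made patient by patient. The documents do not say why such medication would be started, so the link to poor response is an assumption.
- **Weight.** The analysis is conditional and outside the gatekeeping. That is correct, and it limits the seriousness.
- **Purpose.** It is tempting to say that the regulator wanted proof that background treatment does not explain the result. The amendment log says only that the analysis was suggested; the purpose would be an inference.

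A reader might also infer that the sponsor will choose strata unblinded. The text does not say so. It is silent on unblinding, although comparing use by arm needs allocation at least at group level.

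**Conclusion.** The point holds as a weakness in how the subgroups are defined and when they are chosen. By the plan's own definitions, trigger and strata can include medication started after randomisation, and nothing requires the choice to precede unblinding. The within-stratum comparisons then lack the protection of randomisation.

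Neither size nor direction can be fixed from the documents. With a uniform true effect of 0.35, the assumed scenarios give 0.24 to just under 0.35 in non-users and 0.20 to 0.36 in users. With no true effect and use differing by 10–20 points, the per-stratum one-sided error ran from 0.002 to 0.14 instead of 0.025. All of this rests on assumed usage rates, correlations and prescribing rules.

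It would be wrong to conclude that the trial's main result is at risk: the co-primary superiority tests and the non-inferiority tests do not use these strata. The change should be made, but the confirmatory analysis does not depend on it.

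**What to change.** Replace SAP 4.9.1.6 with a rule along these lines:

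- Define subgroups by medication ongoing at the first dose: systemic antibiotic, corticosteroid and bronchodilator, each yes/no.
- Fix the classes and a minimum stratum size before unblinding. A stratum holding 30% of 111 patients per arm has about 44% power for 0.35 (SD 0.79, one-sided 0.025), so small strata say little.
- Label the results exploratory.
- Report medication started after the first dose descriptively by arm, not as a stratum.
- Base the baseline flag on the recorded start date. SAP 4.14.7.1 sets a partial start date to the first-dose date when its known parts match that date, and does the same for most missing start dates. A plain start-before-first-dose rule applied to the imputed dates would misclass some of these as new. One option is to class them as ongoing at baseline unless the known parts show a later start, with a sensitivity check. The rule should also cover a recorded start on the day of the first dose.

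Start dates are already collected, so no new data are needed. The cost is a short SAP revision, one derived flag with its date rule, and one descriptive table.

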4.9.2 Primary Efficacy Analysis

The co-primary efficacy endpoints are: "the change from baseline to day 7 in sputum viscosity score" and "the change from baseline to day 7 in expectoration difficulty score" and they will be analyzed on the mITT and PP populations by means of stratified Mann-Whitney U Statistics for testing the hypotheses of superiority of NAC versus placebo (primary objective) and by means of a modified Mann-Whitney U Statistics (Rothmann, et al., 2012) for testing the hypotheses of non-inferiority of NAC versus ambroxol (key secondary objective) assuming a margin (i.e. δ') of non-inferiority equal to 0.30.

Statistically significant results will be needed on both mITT and PP populations to accept the hypothesis of non-inferiority of NAC versus ambroxol. Non-inferiority will be declared if the one-sided confidence interval will be within the interval $[1/2 - \delta'', 1]$ so, equivalently, the lower limit of the confidence interval will be greater than $1/2 - \delta''$, where δ'' is the non-inferiority margin converted on a probability scale from a point scale δ' . Details of the converting margin can be found in Appendix 4.14.6. Note that the one-sided confidence interval will be conducted depending on the outcome of the first gatekeeper procedure for the superiority contrasts.

In addition, for all superiority test in efficacy analysis, Hodges Lehmann point estimate of the median treatment differences together with associated two-sided 95% confidence intervals will be computed using nonparametric bootstrap; For all non-inferiority tests in the efficacy analysis, point estimates of treatment differences in probability scale together with associated one-side confidence interval will be provided. Nonparametric bootstrap point estimates of treatment differences in probability scale together with two-sided 95% confidence intervals will also be computed. Details of bootstrap can be found in Appendix (Section 4.14.2).

The following summaries of testing the hypotheses of superiority of NAC versus placebo and non-inferiority of NAC versus ambroxol will be provided:

- A summary of the change from baseline to day 7 in sputum viscosity score using the mITT population, in which the missing data will be handled using the MVTF
- A summary of the change from baseline to day 7 in expectoration difficulty score using the mITT population, in which the missing data will be handled using the MVTF

- A summary of the change from baseline to day 7 in sputum viscosity score using the PP population, in which the missing data will be handled using the MVTF
- A summary of the change from baseline to day 7 in expectoration difficulty score using the PP population, in which the missing data will be handled using the MVTF

The following sensitivity analyses will be provided:

- A summary of p-value of the superiority and non-inferiority tests for the change from baseline to day 7 in sputum viscosity score using the mITT population and PP population, in which the missing data will be handled using the EM algorithm
- A summary of p-value of the superiority and non-inferiority tests for the change from baseline to day 7 in expectoration difficulty score using the mITT population and PP population, in which the missing data will be handled using the EM algorithm
- A summary of p-value of the superiority and non-inferiority tests for the change from baseline to day 7 in sputum viscosity score using the mITT population and PP population, in which the missing data will be handled using the LOCF
- A summary of p-value of the superiority and non-inferiority tests for the change from baseline to day 7 in expectoration difficulty score using the mITT population and PP population, in which the missing data will be handled using the LOCF

The test statistics for the superiority and non-inferiority tests can be found in the Appendix (Section 4.14.5 and 4.14.6).

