4.9 Efficacy Evaluation

The co-primary efficacy endpoints are: “the change from baseline to the 1-week treatment in sputum viscosity score” and “the change from baseline to the 1-week treatment in expectoration difficulty score” and will be analyzed using the mITT and PP populations. The primary study objective will be assessed by testing superiority of NAC compared to placebo and will be achieved if at least one of the two co-primary end-points will be found statistically significant.

The key secondary objective will be assessed through the analysis of non-inferiority of NAC compared to ambroxol and, similarly, will be reached if at least one of the two co-

primary end-points will be found statistically significant for both the mITT and PP populations. Details will be found in section 4.9.1.4.

Conversely, the analyses of the remaining secondary efficacy endpoints will be treated as non-key secondary objectives since they will be performed only to support primary endpoints findings.

A by-subject listing of all efficacy variables (score of sputum viscosity, expectoration difficulty, sputum color and cough, and sputum volume) will be provided using the mITT population (Section 4.4.3).

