4.14 Appendix

4.14.1 Hochberg procedure

In the case the co-primary endpoints for the superiority of NAC versus placebo are statistically significant (first gatekeeper), in the second gatekeeper for the family of non-inferiority tests the Hochberg procedure for adjustment of multiple comparisons across the two co-primary endpoints will be performed. The Hochberg procedure assumes p-values are independent and uniformly distributed under respective null hypotheses and control the familywise error rate calculated in step-up fashion.

Suppose test m null hypotheses and denote the ordered p-values as $p_{(1)} \leq \dots \leq p_{(m)}$, the Hochberg-adjusted p-values $\tilde{p}_{(1)} \leq \dots \leq \tilde{p}_{(m)}$ are obtained from:

$$\tilde{p}_{(i)} = \begin{cases} p_{(m)} & \text{for } i = m \\ \min(\tilde{p}_{(i+1)}, (m - i + 1)p_{(i)}) & \text{for } i = m - 1, \dots, 1 \end{cases}$$

The SAS syntax of Hochberg procedure is specified as follows:

```
PROC MULTTEST INPVVALUES=<input_raw_pvalue> OUT=<output_adjust_pvalue>
HOCHBERG;
RUN;
```

Where `input_raw_pvalue`= “the raw p-value calculated”.
`output_adjust_pvalue`= “the adjusted p-value output”.

The procedure of MULTTEST will compute the adjusted p-value and can be tested on both co-primary endpoints with an overall probability α set to 0.025 (one-tailed).

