    delta2= delta1*sqrt(&UT2+&UC2)/sqrt(&Std_RT**2+&Std_RC**2) ;  
    p_10=0.5- delta2 ; /* defined margin*/  
    Z_p1=(p_1-p_10)/e_p1; /* modified Wilcoxon-Mann-Whitney test  
    statistics*/  
  
    p_p1=1-probnorm(Z_p1); /*p value for P_1*/  
  
    lower limit_1=p_1-1.96* e_p1; /* Depends on results of primary  
    endpoint, here is the sample code of one side 97.5% lower CI of  
    modified Wilcoxon-Mann-Whitney test statistics */  
    upper limit_1=1; /* Upper CI of modified Wilcoxon-Mann-Whitney  
    test statistics*/  
  
    lower limit_2=p_1-2.24* e_p1; /* Depends on results of primary  
    endpoint, here is the sample code of one side 98.75% lower CI of  
    modified Wilcoxon-Mann-Whitney test statistics */  
    upper limit_2=1; /* Upper CI of modified Wilcoxon-Mann-Whitney  
    test statistics*/  
  
run;
```

where `input_data` = “individual efficacy data of changing from baseline”

trt01pn = “treatment group, 1 stands for test group; 2 stands for control group”
chg = “change from baseline score of ordinal categorical 4-point scales starting from 0(normal) to 3(worst) of sputum viscosity score, expectoration difficulty score, sputum color score, and cough severity score”

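### SAP 4.9.2 adds an interval rule for declaring non-inferiority that does not match the Hochberg step of 4.9.1.4 when both superiority contrasts succeed

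*SAP*

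**What the plan says.** **The p-value rule.** SAP 4.9.1.4 splits the non-inferiority test by the superiority result in mITT. If both superiority contrasts succeed (2a), both endpoints are tested at overall one-sided 0.025 "with the adjustment for multiple comparisons across the two co-primary endpoints performed according to Hochberg". If only one succeeds (2b), that endpoint alone is tested and needs p ≤ 0.0125. SAP 4.14.1 codes the Hochberg step: "The procedure of MULTTEST will compute the adjusted p-value and can be tested on both co-primary endpoints". Both populations are required: "Statistically significant results will be needed in both the mITT and PP populations to accept the hypothesis of non-inferiority of NAC versus ambroxol". Protocol 20.4.5 has the same two branches.

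**The interval rule.** SAP 4.9.2 gives a declaration rule of its own: "Non-inferiority will be declared if the one-sided confidence interval will be within the interval" bounded by 1/2 − δ'' and 1. It adds that "the one-sided confidence interval will be conducted depending on the outcome of the first gatekeeper procedure for the superiority contrasts". The sample code in 4.14.6 computes one p-value and two lower limits, with multipliers 1.96 (97.5%) and 2.24 (98.75%). Each limit is commented as depending on the primary-endpoint results, but the result that selects each one is not given.

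**The links between them.** SAP 4.9 says the key secondary objective is met if at least one endpoint is "found statistically significant for both the mITT and PP populations. Details will be found in section 4.9.1.4". SAP 4.9.1.4 says the "strategy described above will also be applied to control the coverage of confidence intervals at the two-tailed 95% nominal level". No text or code turns that sentence into a rule for the one-sided limits.

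**The concern.** Hochberg's verdict on one endpoint depends on the other endpoint's non-inferiority p-value. The interval rule of 4.9.2 takes its level from the superiority outcome only, so it cannot carry that information. In branch 2a the SAP therefore has two statements of how non-inferiority is declared, and they can disagree for the same data.

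At stake is the key secondary claim of a registration trial. If the more liberal limit decided, a false non-inferiority claim would be more likely than planned. If the stricter one decided, an endpoint that the planned procedure accepts could be refused. Branch 2b is not in conflict if the 98.75% limit is used there.

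**Working it through.** **Inputs** (SAP 4.11): 100 per arm; margin 0.30; SD 0.79 and 0.77; endpoint correlation 0.31; NAC–placebo difference 0.35; stated power close to 93% for superiority and 82% for non-inferiority. The documents give neither the true NAC–ambroxol difference nor the PP fraction. Both are assumed below.

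**1. The plan's own figures.** Simulation with Mann-Whitney superiority tests at 0.0125, non-inferiority t-tests, Hochberg in 2a, p ≤ 0.0125 in 2b and NAC equal to ambroxol gives disjunctive power of 93.6% for superiority and 80.6% for non-inferiority. A larger simulation on normal arm means gives 81.6% for non-inferiority. Both agree with the stated figures to within 2 points, so the planned power rests on Hochberg.

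**2. What clearing a limit means.** In 4.14.6, Z = (p̂ − (0.5 − δ''))/e, and the p-value is one minus the normal probability of the same Z. The lower limit is p̂ − c·e. It exceeds 0.5 − δ'' exactly when Z > c:
- c = 1.96: raw p below 0.025.
- c = 2.24: raw p below 0.01255. The exact quantile for 0.0125 is 2.2414.

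**3. Two worked cases in branch 2a.** With p(1) ≤ p(2), the Hochberg-adjusted values are p(2) and min(p(2), 2·p(1)).

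| Raw p-values | Adjusted p-values | Hochberg at 0.025 | 97.5% limits | 98.75% limits |
|---|---|---|---|---|
| 0.020, 0.030 | 0.030, min(0.030, 0.040) = 0.030 | none | one | none |
| 0.020, 0.024 | 0.024, min(0.024, 0.040) = 0.024 | both | both | none |

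**4. Error in one population, both superiority contrasts passed, both nulls at the margin.** Let Φ₂ be the bivariate normal distribution function with correlation 0.31.
- 97.5% limits: 1 − Φ₂(1.96, 1.96) = 1 − 0.9525 = 4.75%.
- 98.75% limits: 1 − Φ₂(2.2414, 2.2414) = 1 − 0.9758 = 2.42%.
- Hochberg: 2.42% plus the probability that both statistics lie between 1.96 and 2.2414 (0.05%) = 2.46%, from unrounded values.

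**5. Error with the superiority stage and both populations.** This used 2,000,000 simulated trials per setting, superiority on mITT, PP as a random subset of mITT, Hochberg within each population, and the same endpoint required in both. Entries are 97.5% limits / 98.75% limits / Hochberg.

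| PP as share of mITT | NAC–placebo 0.35 | NAC–placebo 0.5 |
|---|---|---|
| 90% | 3.2 / 1.6 / 1.7% | 3.4 / 1.7 / 1.7% |
| 80% | 2.6 / 1.3 / 1.4% | 2.8 / 1.3 / 1.4% |
| 77% | 2.5 / 1.2 / 1.3% | 2.7 / 1.2 / 1.3% |
| 70% | 2.2 / 1.1 / 1.1% | 2.4 / 1.1 / 1.1% |

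**6. How often the rules differ** (NAC equal to ambroxol, NAC–placebo 0.35, PP 90%). The 97.5% limits depart from Hochberg in 3.5% of trials, and each of these changes the overall claim. The 98.75% limits depart on at least one endpoint in 9.5%, but change the overall claim in only 1.0%.

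**The case against.** The strongest reply is that the SAP already shows which rule governs. Section 4.9 defines success on the key secondary objective and refers to 4.9.1.4, where the criteria are p-values. Section 4.14.1 codes Hochberg. Protocol 20.4.5 has the same procedure, and SAP 4.12 does not list it among the changes. The sentence before the interval rule in 4.9.2 also asks for statistical significance. On this view the interval sentence only puts the margin on the probability scale. In addition, the two coded levels are Hochberg's two cut-offs, and used together as a step-up rule they reproduce it exactly.

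Much of this stands. A reader might infer that the SAP leaves the two non-inferiority tests unadjusted, or gives no hint of which rule decides. The documents support neither inference. What remains is that 4.9.2 uses declaration wording, ties its level to the superiority result alone, and is not made subordinate to 4.9.1.4. The step-up pairing of the limits is written nowhere.

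Two points about size also stand. The 4.75% is for a single population, which the SAP never lets decide non-inferiority. And the two-population figures treat PP as a random subset, whereas PP excludes patients for low compliance or major deviations, so the true overlap may differ.

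**Conclusion.** The conflict is real and confined to branch 2a. Neither limit used alone reproduces Hochberg: 97.5% limits can only over-claim relative to it, and 98.75% limits can only under-claim. The cross-reference in 4.9 favours Hochberg, so this is a contradiction to remove and not evidence that error control is lost.

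Error control would suffer only if 97.5% limits were used in branch 2a and allowed to decide. The error would then be 4.75% against 2.46% in one population, or about 2.2–3.4% against 1.1–1.7% with both populations required. Those ranges assume correlation 0.31, both nulls at the margin, PP a random 70–90% of mITT, and a NAC–placebo effect of 0.35 or more.

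A reader might take a fixed PP share, such as 77%, as the point where 2.5% is crossed. That holds only at an effect of 0.35; at 0.5 or more the crossing lies between 70% and 77%. With 98.75% limits the error is controlled. The primary superiority decision is unaffected. This should be fixed.

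**What to change.** In SAP 4.9.2, state that non-inferiority is decided only by the Hochberg-adjusted p-values of 4.9.1.4 and 4.14.1, or by p ≤ 0.0125 when only one superiority contrast succeeds. Apply this separately in mITT and in PP, and require the same endpoint to succeed in both. State that the one-sided limits report that decision, as follows:
- **Both superiority contrasts succeed:** within each population, report 97.5% limits for both endpoints if both exceed 1/2 − δ'' at that level; otherwise report 98.75% limits for both.
- **Only one succeeds:** report the 98.75% limit for that endpoint.

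Put this pairing in the 4.14.6 code and replace 2.24 with the exact normal quantile (2.2414), so that limit and p-value agree at 0.0125. In the simulation of step 1 the paired limits matched Hochberg in every trial.

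**Cost.** A few sentences and small code edits. Where a 98.75% limit replaces a 97.5% one, it lies about 14% further from the estimate (2.24/1.96 = 1.14). Power is unchanged from the planned Hochberg procedure. It is lower than under an unadjusted 97.5% reading: 81.6% against 84.2% in one population, and 76.4% against 79.9% with both populations at PP 90%, taking NAC equal to ambroxol and NAC–placebo 0.35. Against a 98.75% reading it is slightly higher (76.4% against 75.4% with both populations).
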